Principal Investigator	Signature	Date	

LIST OF ABBREVIATIONS

AE	Adverse Event	
BG	Blood Glucose	
CI	Chief Investigator	
CNORIS	Clinical Negligence and Other Risks Indemnity Scheme	
GCP	Good Clinical Practice	
ICF	Informed Consent Form	
ISF	Investigator Site File	
PI	Principal Investigator	
REC	Research Ethics Committee	
SOP	Standard Operating Procedures	
SMF	Study Master File	
T1D	Type 1 Diabetes	
PA	Physical Activity	

SUMMARY/SYNOPSIS

Study Title	Knowledge and barriers related to physical activity in type 1 diabetes (KBPA T1D)		
Study Design	Survey		
Study Population	Patients with Type 1 Diabetes		
Sample Size	At least 50 (and up to a maximum of 500)		
Planned Study Period	Eight (8) weeks from launch of survey		
Follow up phase duration	None	None	
Primary	Objectives Determine main barriers to physical activity	Outcome Measures Survey	
Secondary	Relate health benefits to physical activity and T1D Determine better practices for healthcare practitioners related to physical activity and T1D Determine better recommendations for participation in sport Determine socioeconomic impacts related to physical activity and diabetes	Survey	
Inclusion Criteria	Person with Type 1 Diabetes Aged 18 or over Able to read and write in English		
Exclusion Criteria	Participant is unable to complete survey		

1 INTRODUCTION

2 BACKGROUND & RATIONALE

There are >300,000 people with diabetes in Scotland, approximately 10% of these have Type 1 Diabetes (T1D). Current research indicates that populations with diabetes are not as active as their counterparts without diabetes. To address this, it is important to determine the main barriers to PA that T1D patients experience [1]. PA has been demonstrated to possess numerous health benefits for both the general population as well as for patients with T1D [2]. Regular PA can lessen the risk of cardiovascular disease, lower HBA1c, and improve body composition, cardiorespiratory fitness, endothelial function, and blood lipid profile (i.e. triglycerides, total cholesterol) within patients with T1D [2]. Given that cardiovascular disease is the leading cause of morbidity and mortality in people with T1D, the cardiometabolic improvements seen from increased PA are critical for preventing the complications of diabetes [3].

It has been demonstrated that a majority of people with diabetes are overweight or obese, suffer from hypertension, and are not physically active [2]. Many planned interventions to promote PA have failed to significantly change individuals' behaviour [4]. In order to improve the effectiveness of public health interventions, factors that impede the regular practice of PA must be identified [5]. The presence of perceived barriers decreases the likelihood of engaging in preventative health practices, especially if those barriers outweigh the perceived benefits of doing so [5]. The most commonly reported barriers to physical exercise are fear of hypoglycaemia, interruptions to work schedule, loss of glycaemic control in type 1 diabetes, and low fitness level [4]. In addition, there exists a knowledge gap in the diabetes population regarding insulin pharmacokinetics, hypoglycaemic prevention and PA [4][6]. Furthermore, social support has been shown to have a powerful inverse relationship with PA participation [4]. Other common barriers to PA seen in patients with T1D include lack of time, work-related factors, difficulties with access to facilities (distance and cost), lack of motivation, low confidence (embarrassment about body image and fear of failing), weather, and health-specific barriers (low levels of knowledge about managing T1D around PA and T1D complications) [6].

Determining the most pertinent barriers to PA experienced by those with T1D is an initial step to inform planning of suitable interventions based on PA. Clinical care teams must have current information available to discuss PA with T1D patients. With that information, clinical care teams can increase the activity levels of their patients, while also increasing their quality of life and positively impacting their disease prognosis.

One of the most relevant studies published to date - one that also formed the basis of this research project's survey - was published in 2006 by Dubé and colleagues [7]. They sought to validate an 11-item Likert-type self-administered questionnaire based upon the most frequently reported and impactful barriers to PA experienced by patients with T1D. Brazeau et al., (2008) then used the 11-item questionnaire validated by Dubé et al., to assess sociodemographics and T1D treatment using a 44-item questionnaire [8]. Similarly, Wadén and colleagues undertook a cross-sectional analysis of 1,945 patients with T1D to determine the associations between PA and microvascular and macrovascular diabetes complications [9]. They determined that lower activity levels were associated with impaired renal function, and an increasing degree of proteinuria, retinopathy, and cardiovascular disease [9]. Makura et al., (2013) also assessed the associations between T1D and microvascular outcomes within the Diabetes Control and Complications Trial [10]. Tielemans et al., (2013) within a prospective cohort study of 3250 patients, assessed the activity levels of patients in 16 European countries and concluded that 36% of patients were performing none to only mild PA [11]. Lascar et al., (2014) found six main barriers to PA in their qualitative study of 26 patients via a semi-structured interview [12]. Those barriers included lack of time, work-related factors, difficulties with access to facilities (distance and cost), lack of motivation, low confidence (embarrassment about body image and fear of failing), weather, and health-specific barriers (low levels of knowledge about managing T1D around PA and T1D complications) [12]. They also noted that interviewees expressed frustrations at not understanding why in certain situations their blood glucose (BG) rose with PA and felt that having more information around how PA can affect BG levels would

encourage them to exercise [12]. The most recent study regarding barriers to PA in patients with T1D was a qualitative study conducted by Kennedy et al., (2018) [13]. Kennedy and colleagues (2018) focused their study on newly diagnosed patients with T1D and thus framed their questions around any changes to their PA after diagnosis [13]. 33% of participants reported a reduction in the amount of time they spent physically active, and 47% of participants reported a change in the type of PA or a reduction in the intensity of PA within which they participated [13]. Most participants were unaware of the minimal PA guidelines or uncertain as to the amount recommended. Two main subthemes emerged related to barriers to PA: medical barriers and influence of healthcare practitioners [13]. 60% of participants reported hypoglycaemia as a medical barrier to PA, while 47% reported lack of knowledge or confidence of managing T1D around PA, and 27% of participants mentioned the need to plan for PA with T1D as a discouraging factor [13].

The main aim of this research project is to identify the most common barriers to PA experienced by those with T1D. The educational goal of this research project includes public health information to be analysed and shared with the T1D clinics that host the questionnaire invitations. This sharing of knowledge will ultimately lead to an improvement in treatment outcomes and more appropriate physical activity prescriptions given to the diabetic population. In garnering a more active diabetic population, common comorbidities associated with T1D can be lessened in severity or reduced in incidence.

The most commonly experienced barriers to PA have been only studied within a minimal amount of academic papers, and thus the field lacks research quantity. As physical activity research increases in popularity, researchers will begin to question why specific populations are not as active as others. Thus, they will need to identify barriers to physical activity, and this research project will aid in accomplishing that goal. PA is becoming more prevalent in popular culture, and rising levels of inactivity and obesity are being reported and addressed. General populations will also seek to identify the most prevalent barriers to PA. Understanding why a particular population is not as active as another is important for society at large. A member of the non-diabetic population may also experience the same barriers as the diabetic population, and thus this research project can benefit society as a whole.

3 STUDY OBJECTIVES & OUTCOMES

A patient facing survey will be used to determine the barriers to PA.

The primary objective is to:

Determine barriers to PA in people with T1D

The secondary objectives are to:

- Relate health benefits to PA and T1D
- Determine better practices for healthcare practitioners related to PA and T1D
- Determine better recommendations for participation in sport
- Determine socioeconomic impacts related to PA and diabetes

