4.2 STUDY DESCRIPTION

This study will consist of a survey of five main sections as well as an introductory 'Definitions' section.

The 'Definitions' section will outline specific terms and phrases used within the survey with which some participants may be unfamiliar.

Section 1, 'Demographics' will ask participants their age range, gender, location, length of T1D diagnosis, and most recent HbA1c.

Section 2, 'Physical Activity Barriers' will ask participants to indicate how likely an item would keep them from participating in PA during the next six months. Items will include potential barriers to PA.

Section 3, 'Diabetes Management' will ask participants about their current treatment of their T1D, the information they discuss in clinic visits and their knowledge on PA information resources and condition management around PA.

Section 4, 'Exercise' will ask participants about their participation frequency of various forms of exercise, as well as changes from euglycemia around exercise.

Section 5, 'Sport' will ask participants about their participation frequency of sport, as well as changes from euglycemia around sport. It will also ask participants to indicate the degree to which they agree with statements pertaining to PA enjoyment, and the effects of their condition on their sport participation.

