6 DATA COLLECTION & MANAGEMENT

6.1 DATA COLLECTION

There will be one survey window of approximately 8 weeks.

People receiving the survey online can return the survey at any time in that window. People receiving the survey in clinic must decide whether or not to complete it at the time or shortly thereafter. Time and place of completion can be decided by the participant.

The survey content will provide the entire source data for the research study.

If a patient returns a survey but later wishes to be withdrawn this will not be possible as the data will be anonymous.

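### As the survey is described, no item measures socioeconomic position, so the secondary objective on socioeconomic impacts has no matching variable

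*Protocol*

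**What the plan says.** Protocol section 3 lists four secondary objectives. The last is "Determine socioeconomic impacts related to PA and diabetes". The synopsis repeats it as "Determine socioeconomic impacts related to physical activity and diabetes" and gives the survey as the only outcome measure for the secondary objectives.

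Section 4.2 outlines a survey of five parts, preceded by a page of definitions:

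- Survey Section 1 (demographics) "will ask participants their age range, gender, location, length of T1D diagnosis, and most recent HbA1c".
- Survey Section 2 asks how likely each of a set of items is to keep the respondent from being active. Of the items it says only: "Items will include potential barriers to PA".
- Survey Section 3 "will ask participants about their current treatment of their T1D, the information they discuss in clinic visits", and also covers knowledge of activity resources and of managing the condition around activity.
- Survey Section 4 asks about "participation frequency of various forms of exercise, as well as changes from euglycemia around exercise".
- Survey Section 5 asks the same about sport, and asks for agreement with "statements pertaining to PA enjoyment, and the effects of their condition on their sport participation".

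On data sources, section 6.1 states: "The survey content will provide the entire source data for the research study". Section 4.4 describes a single completion, the synopsis gives no follow-up, and section 5.2 makes the survey anonymous with no identifying data.

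**The concern.** To report how activity, barriers or the burden of diabetes vary with socioeconomic circumstances, a study needs at least one measure of those circumstances for each respondent. The outline in section 4.2 does not name one, and no other source could provide it.

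This is not a detail to leave to an analysis plan. Section 7.2 has that plan written before the survey closes, which allows it to be written while responses are already arriving. In any case, it can only work with what the questionnaire asked. If the survey runs as outlined, the study report will either say nothing on a stated objective or draw socioeconomic conclusions from items that were not designed to support them.

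**Working it through.** The plan gives no figure to reproduce on this point and no formula applies. The check is a mapping from the objective to the data.

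**Step 1: what the objective needs.** The protocol does not define socioeconomic impacts. On the usual reading, the variable needed is a measure of respondents' socioeconomic position, such as education, employment, income or area deprivation.

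**Step 2: what each survey part is described as collecting (section 4.2).**

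| Survey part | Described content | Socioeconomic measure named? |
|---|---|---|
| 1 Demographics | Age band, gender, place, time since diagnosis, latest HbA1c | No; place is the nearest item |
| 2 Barriers | Likelihood that each item would prevent activity; items not listed | No; cost or work items are possible but not stated |
| 3 Diabetes management | Treatment, clinic discussions, knowledge | No |
| 4 Exercise | Frequency, glucose changes | No |
| 5 Sport | Frequency, glucose changes, enjoyment, effect of the condition | No |

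The count is 0 of 5 parts naming a socioeconomic measure. The demographics entry reads as a closed list, with no wording to suggest that its variables are only examples.

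**Step 3: other routes to the variable.**

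- Other data sources: none, since section 6.1 makes the survey the whole of the source data.
- Linkage to records: ruled out by section 5.2, because no identifying data are held. The unique number on each survey ties together the answers on that survey. It does not lead back to a person, and section 6.1 confirms this by saying that a returned survey cannot be withdrawn.
- Recontact or a second survey: ruled out by single completion and no follow-up.

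**Step 4: the two nearest items.**

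- *Location.* Its level of detail is not stated. Section 5.1 recruits directly in Scotland, and through social media in the rest of the UK and other English-speaking countries. The protocol names no area-level index and does not say that location is meant to stand for socioeconomic position.
- *Barrier items.* The background in section 2 mentions work, and the cost and distance of facilities, as known barriers, so survey Section 2 may ask about them. Such answers would record a perceived barrier, which is the primary objective. They would not record the respondent's own circumstances, so they could not show how barriers differ by those circumstances.

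**Result.** One of four secondary objectives has no variable assigned to it in the survey as described, and none can be supplied after return.

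**The case against.** The strongest reply is that section 4.2 is a summary. Each survey part gets one or two sentences, and the questionnaire is not among the documents. The barrier items are left open, and the background says the survey was based on an existing 11-item barrier questionnaire, so cost, work or access items are plausible. The objective is also undefined. It speaks of impacts, not of differences by socioeconomic position, and could be read as the perceived cost, work and access burden around activity. On that reading survey Section 2, and the statements in Section 5 about the effect of the condition on sport, might answer part of it. Location might likewise allow an area-level description among Scottish respondents, if it is recorded finely enough.

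Much of this stands. A reader might infer that the objective cannot be answered at all, or that nothing relevant could be recovered once the survey closes. The documents do not support either inference: location is collected, and the barrier items are not listed. What the reply does not change is that the demographics list contains no measure of socioeconomic position, that no other survey part names one, and that the protocol does not give location or the barrier items this role.

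A reader might also infer that the barrier results are confounded for lack of a socioeconomic variable. That does not follow. The only analysis stated in section 7.2 is descriptive statistics for binary or tick-box responses, with no adjusted or causal comparison planned.

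**Conclusion.** The point holds in this form: as the survey is described, the socioeconomic objective has no matching variable, and the anonymous one-off design means none can be added after return. Existing items could give partial information at most.

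The extent is one of four secondary objectives. Severity is moderate. The primary objective, identifying barriers, does not depend on a socioeconomic measure, and the documents give no reason to treat this as a threat to it.

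The conclusion assumes that section 4.2 reflects the questionnaire's content, in particular that the demographics list is complete. If the questionnaire already holds socioeconomic items, the fault reduces to a protocol that does not list them or tie them to the objective.

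**What to change.** Before launch, choose one of three changes.

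1. **Add the measure (preferred).** Put two or three tick-box items in survey Section 1, for example highest education, employment status, and banded income or financial strain with a prefer-not-to-say option. List them in section 4.2 and state that barrier frequencies will be reported descriptively by these items. Banded answers fit the anonymous design.
2. **Narrow the objective.** If survey Section 2 contains cost, work and access items, reword the objective to perceived barriers of that kind and name the items that serve it. If location is also meant to contribute, state its level of detail and how it will be used.
3. **Delete the objective** from both the synopsis and section 3, so that no socioeconomic conclusion is drawn.

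Option 1 makes the survey slightly longer and brings some item non-response. The breakdowns may also be thin. Assuming three equal bands, the planned 50 to 500 respondents give 50/3 ≈ 17 to 500/3 ≈ 167 per band, so at the lower end the results would be descriptive only. Options 2 and 3 cost a line of text. Any of the three needs the amendment approvals set out in section 12.1. Timing matters most for option 1, because it cannot be done for surveys already returned.

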4 STUDY DESIGN

4.1 INTERVENTION

This study will use an anonymous survey (both online and paper-versions) to assess patient opinions and knowledge and capture data about perceived barriers to PA. The survey has been reviewed by a Public and Patient Involvement (PPI) group.

4.2 STUDY DESCRIPTION

This study will consist of a survey of five main sections as well as an introductory 'Definitions' section.

The 'Definitions' section will outline specific terms and phrases used within the survey with which some participants may be unfamiliar.

Section 1, 'Demographics' will ask participants their age range, gender, location, length of T1D diagnosis, and most recent HbA1c.

Section 2, 'Physical Activity Barriers' will ask participants to indicate how likely an item would keep them from participating in PA during the next six months. Items will include potential barriers to PA.

Section 3, 'Diabetes Management' will ask participants about their current treatment of their T1D, the information they discuss in clinic visits and their knowledge on PA information resources and condition management around PA.

Section 4, 'Exercise' will ask participants about their participation frequency of various forms of exercise, as well as changes from euglycemia around exercise.

Section 5, 'Sport' will ask participants about their participation frequency of sport, as well as changes from euglycemia around sport. It will also ask participants to indicate the degree to which they agree with statements pertaining to PA enjoyment, and the effects of their condition on their sport participation.

4.4 STUDY ASSESSMENTS

One off completion of a survey.

4.5 STUDY SAFETY ASSESSMENTS

As this is a patient facing survey safety assessments are not required as there is no risk of harm to the participant.

4.6 STUDY POPULATION

Patients with T1D are required to complete the survey.

4.7 NUMBER OF PARTICIPANTS

At least 50 (to a maximum of 500).

4.8 INCLUSION CRITERIA

- Type 1 Diabetes
- Aged 18 or over
- Able to read and write in English

4.9 EXCLUSION CRITERIA

Participant is unable to complete survey

5 PARTICIPANT SELECTION AND ENROLMENT

5.1 IDENTIFYING PARTICIPANTS

Participants will be recruited to attempt the survey by various means.

We will utilise the NHS Research Scotland (NRS) Diabetes Research Network permission to contact database of people with who have expressed a willingness to be involved in research. This register has a large cohort of people with T1D who can be approached directly via email or letter (phone contact will not be used). People with T1D in Scotland who are part of this

system will be approached via email or letter. Attempts will be made to approach as many people as possible with the limitations of available resources.

In addition, we will approach patients in diabetes clinics within NHS Tayside who are waiting for a routine eye screening or clinical care appointments. Posters will also be used within diabetes clinics to refer the public towards the online survey location or to acknowledge the paper copies of the survey available within the clinic.

We will also advertise the survey widely on social media platforms to encourage widespread participation (invitation to participate for those with Type 1 Diabetes living in England, Wales, Northern Ireland and other English speaking countries).

The patient information sheet may be provided separately in paper form but is also integrated into the web-based version of the survey along with the consent so that the patient information sheet, consent and survey can be assessed either electronically or in paper form.

5.2 CONSENTING PARTICIPANTS

Participants that agree to or self-select to take part in the study will be provided with a link to the survey, including a PIS. Information and Consent will be embedded within the start of the survey. Implied consent will be assumed by the return of the survey.

There will be an 8-week window within which surveys should be returned or completed. Participants are under no obligation to complete this.

The study will be anonymous. Each survey will be given a unique identification number to link individual responses. No personally identifiable data will be collected.

5.3 INELIGIBLE AND NON-RECRUITED PARTICIPANTS

Individuals who are found to be ineligible for the study, will be thanked for their interest (if it is possible to do this), and no further data will be collected. Survey data provided by ineligible participants will be removed.

